Mixed-effects linear regression model was used to assess changes in glucose, insulin, and c-peptide profile over the course of 180 minutes and the difference of first mealtime at 8:00AM, 12:00PM, and 4:00PM univariately. The difference of mealtime over the course of 180 minutes on glucose, insulin and c-peptide levels was assessed by including mealtime as an interaction term in the mixed-effects linear regression model. Due to the skewness of the distribution, differences in glucose, insulin, and c-peptide AUCs over 180 minutes and the insulinogenic index by mealtime were assessed on a logarithmic scale. Profiles that were significantly differ across meal timing were subjected to pairwise comparisons using the false discovery rate based on Simes' method. Changes in profiles were described using beta estimates (β) with its associated 95% confidence intervals and p-values. Pairwise comparisons were presented as percent changes with its associated 95% confidence intervals, unadjusted and adjusted p-values.

The secondary outcome variables included incretin levels and pancreatic hormones, which includes glucagon, pancreatic polypeptide, glucagon-like-peptide-1 (GLP-1), and glucose-dependent-insulinotropic polypeptide (GIP). Mixed-effects linear regression model was used to assess the changes in incretin levels and pancreatic hormones between pre- and post-intervention timepoints. Additionally, mealtime difference on the changes in incretin levels and pancreatic hormones was assessed by including an interaction term in the model, and these variables were analyzed on logarithmic scale. The distributions of incretin levels and pancreatic hormones were described in median and interquartile range by pre- and post- intervention timepoints. The paired difference of pre and post was described using median and 95% confidence intervals by mealtime. Statistical significance was set at 0.05 with two-sided test and all statistical computations were performed in Stata/SE 18.0 (StataCorp, College Station, TX).

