The implementation steps of the proposed RCT are as follows: **(1)** The staff will introduce the study to all eligible participants either in person or virtually and consent interested families for the study; **(2)** All participants and their families will complete baseline study surveys in REDcap; **(3)** All participants and their families will receive training on the use and application of the CGM, which is FDA approved in patients 2 years and older. All equipment required for the duration of the study will be distributed to the participants in-person. **(4)** All participants will be randomized to the order in which they consume their test meal. Test meals will be consumed on different mornings at least three days apart after a 16-h fasting period. Outside of study visits, participants will purchase all their meals as they would normally without alternation to food quality or quantity; **(5)** The study staff will conduct study assessments with participants at baseline and during each test meal study visit (3 total). Participant will be given the option to redo visits with missing lab results (up to 6 total); **(6)** The study staff will perform weekly phone encounters with the participants to assess barriers to study visit attendance and to record any

medication changes or health issues that have occurred in the last 7 days; (7) The PI and research team will meet bi-weekly to monitor all study procedures and oversee data management and analysis.

The implementation steps of the proposed test meals and blood collection are as follows:

- 1) Subjects without a port will have an IV inserted;
- 2) -10 min pre-meal blood sample (5 mL) will be collected from the port or IV for fasting labs;
- 3) Subjects will consume meal; and
- 4) 10 min post-meal blood sample (5mL), 30 min post-meal blood sample (5mL), 60 min post-meal blood sample (5mL), 90 min post-meal blood sample (5mL), 120 min post-meal blood sample (5mL), and 180 min post-meal blood sample (5mL) will be collected from the port or IV post-meal test.

Sharing of Testing Results with Subjects

Study endpoints will be shared with participants upon request via email or over the phone. The PI will review any tests results and if additional medical evaluation is warranted will refer to the primary care providers.

Study Timelines

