Intervention: For the 14 days study period, all participants will maintain their usual lifestyle, including food consumption, physical activity, and sleep patterns. Physical activity and sleep recommendations consistent with the American Academy of Pediatrics guidelines for adolescents will be encouraged but not formally prescribed. **Test Meal Composition:** Each participant will consume three test meals over the study period, administered at three different times of the day. The test meals will be prepared by the dietetic staff at CHLA. The test meal will consist of 770 calories total (one-third of the recommended total daily caloric intake for age, 30% protein, 10% fat, and 60% carbohydrates [CHO]). The test meal will be comprised of a deli sandwich (560 calories, 84 grams of CHO, 10 grams of added sugar) snack bar (100 calories, 17 grams of CHO, 9 grams sugar), and Greek yogurt (110 calories, 16 grams CHO, 7 grams sugar). **Timing of Test Meal Consumption:** There will be three time periods in which the test meal is administered over the study period: 8 AM, 12 PM, and 4 PM. To mimic a TRE model, in which the daily fasting period is extended to 14-16 hours or more all participants will be asked to fast for at least 16-hs prior to their test meal visit. Participants will be asked to not consume any food for 3 hours after the test meal is completed. **Continuous Glucose Monitor.** All participants will be trained to wear a blinded continuous glucose monitor sensor using manufacturer educational materials under the supervision of research staff. Participants will be asked to wear the CGM for 14 days after enrollment. During each study visit, the CGM reader will be connected to the site database to create an individual participant report.

Study Timeline	Q1	Q2	Q3	Q4
Study Start Up				
Hire and train study personnel	X			
Finalize protocol, obtain Institutional Review Board (IRB) approval	X			
Data & document review	X			
Design Test Meal	X			
Apply for CHLA CTSI Biostats Core Pilot Grant	X			
Create Testing Protocol with CTU	X			
Study implementation	X	X	X	
Data Handling				
Data entry/cleaning and analysis		X	X	X
Publications and presentations			X	X
Future Grant Preparation				
R01 and ADA				X

Measurements: The study team will conduct all assessments baseline and each meal consumption visit (3 total). Participant will be given the option to redo visits with missing lab results (up to 6 total). All data will be collected and stored in REDCap.

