Quantifying incretin hormones after test meal from venous sample: Following baseline sampling (0 min), a test meal will be administered. glucagon, GLP-1, GIP, and PP concentrations will be measured in duplicate from plasma samples using Millipore Enzyme-linked Immunosorbent Assays (ELISA) or multiplex assays according to the recommendations of the manufacturer (Birmingham, MA). Total area under the curve (AUC) will be calculated for venous glucagon, GLP-1, GIP, and PP concentrations using the trapezoid methods using GraphPad Prism (Version .01, GraphPad Software Inc, San Diego, CA, USA).

Statistical Consideration: The sample size estimates, and analytical plans were developed under the guidance of [name] who is the Director of the TSRI Biostatistics core and who will also be a mentor on this award. Descriptive statistics, including graphical depictions, will be utilized to assess the degree of symmetry/normality of continuous outcomes and identification of outliers. A ladder of powers approach will be applied to identify the best easy-to-interpret transformation of the continuous outcome variable. The statistical approach will be implemented with and without transformations when appropriate. Data for this 3-treatment, 3-period cross-over design will be analyzed using linear mixed effects model as described in the literature and implemented in STATA 17.1 (College Station, TX) Sensitivity analysis applying weighted least squares regression will follow. Areas under curves (AUC) will be calculated by the trapezoid rule for levels after meal ingestion. Separate AUC will be calculated for the early (initial 30-min) and the total (entire 300-min) responses. This separation of responses in early and total was decided based on previous findings that insulin secretion is progressively increased during these first 30 min after oral nutrient ingestion. Wilcoxon matched paired test will be used for tests of significance between variables obtained during morning, afternoon, and evening meal ingestion. Spearman regression coefficients will be obtained to estimate correlation.

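### The three-period cross-over analysis names no visit-order term and does not place redone visits: a trend across visits costs precision, and could bias the mealtime contrast if redo rates differ by mealtime.

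*Combined protocol and SAP*

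**What the plan says.** Under Statistical Consideration: "Data for this 3-treatment, 3-period cross-over design will be analyzed using linear mixed effects model as described in the literature". The fixed effects are not listed. The same paragraph adds that "Wilcoxon matched paired test will be used for tests of significance between variables obtained during morning, afternoon, and evening meal ingestion".

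The Statistical analysis section at the end of the document describes the model as fitted. It assesses change over 180 minutes and "the difference of first mealtime at 8:00AM, 12:00PM, and 4:00PM univariately". The mealtime difference over those 180 minutes "was assessed by including mealtime as an interaction term in the mixed-effects linear regression model", so the interaction is with minutes after the meal and not with visit. AUCs and the insulinogenic index are compared by mealtime on a log scale. "Statistical significance was set at 0.05 with two-sided test".

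The only covariates named elsewhere are length of fast (Potential Challenges and Alternative Approaches) and Tanner stage (Inclusion Across the Lifespan). Neither is a visit-order term.

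On conduct, meal order is randomised by a blocked, stratified scheme (Risks to Human Subjects, item a), but the set of sequences, block size and strata are not given. Procedures Involved, step 5, states: "Participant will be given the option to redo visits with missing lab results (up to 6 total". The Measurements paragraph repeats this. Neither place says when a redone visit takes place, whether it replaces the first attempt, or how it is analysed.

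**The concern.** A cross-over compares mealtimes within a person across visits, so anything that drifts from visit to visit competes with the mealtime effect. Randomised order protects against this on average, and a period term normally removes what is left. Here no period term is stated.

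The redo option also loosens the protection. A redone meal is eaten later than the attempt it replaces, and whether it is redone depends on missing results and on the participant's choice, both of which arise after randomisation. If redos were commoner at one clock time, that mealtime would sit later in the visit order than randomisation intended, and any drift would enter its contrast with the others. Without redos, the drift would still go into the residual and widen the intervals of a 30-person study.

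**Working it through.** **Inputs from the documents:** n = 30; three mealtimes; three periods; randomised order; redos allowed up to six visits in total; alpha 0.05 two-sided. The documents give no effect size, SD, trend or redo rate, so there is no stated figure to reproduce.

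**Assumptions:** one summary value per visit, within-person SD of 1, and a linear trend of d = 0.3 or 0.5 SD per visit (0.6 or 1.0 SD from the first to the third visit).

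**1. No redos, balanced order.** Every mealtime has mean position 2, so a common trend cancels from the contrast and bias is 0. The trend's sum of squares goes to the residual:

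- Each person contributes (1 + 0 + 1)d² = 2d², so 30 people contribute 60d².
- Residual degrees of freedom: 90 − 30 − 2 = 58.
- Added error variance: 60d²/58.
- d = 0.3: 0.093, and √1.093 = 1.046, so the SE rises by about 5%.
- d = 0.5: 0.259, and √1.259 = 1.122, so the SE rises by about 12%.

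A simulation with 4,000 runs per scenario and six sequences of five participants agrees. The model SE of late minus early goes from 0.256 to 0.269 and 0.289, with type I error of 4.4% and 3.2%.

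**2. Other cases in which the contrast stays unbiased.**

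- Equal 20% redo rates at all mealtimes: bias 0; type I error 4.2% and 3.1%.
- Unblocked random order without redos: bias 0; type I error 5.2% at both trends. Here the test is not conservative, but precision is still lost.
- 22% dropout with equal 20% redo rates, d = 0.5: bias 0; type I error 3.0%.

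**3. Redo rates that differ by mealtime.**

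Bias ≈ (difference in redo rate) × (relative shift in places) × d.

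The shift depends on when redos occur, which the protocol does not say. If they come after all three scheduled visits, a redone meal moves from mean place 2 to place 4, a shift of 2. If a redo directly follows the failed visit, the redone meal moves 1 place, and another meal also moves 1 place half the time, so the relative shift averages 1 − 0.5 = 0.5.

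| Redo rate, early/afternoon/late | d | Formula, shift 0.5 | Formula, shift 2 | Simulated bias, redos last | Type I error, redos last |
|---|---|---|---|---|---|
| 10/10/30% | 0.3 | 0.03 | 0.12 | 0.13 | 6.7% |
| 10/10/30% | 0.5 | 0.05 | 0.20 | 0.21 | 9.0% |
| 10/20/50% | 0.3 | 0.06 | 0.24 | 0.26 | 14.8% |
| 10/20/50% | 0.5 | 0.10 | 0.40 | 0.42 | 25.6% |
| 0/0/50% | 0.3 | 0.075 | 0.30 | 0.30 | 19.0% |
| 0/0/50% | 0.5 | 0.125 | 0.50 | 0.50 | 38.5% |

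Biases are in within-person SD, for late minus early. The simulated values slightly exceed the shift-2 formula where one person may redo several visits.

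**4. With a visit-order term.** Bias is at most 0.007 SD and type I error is 4.4 to 6.0% across all scenarios. The simulated trend and the fitted term were both linear, so this shows what the term does when the trend is modelled correctly.

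**The case against.** The strongest reply is that randomised order already does the work. That is right as far as it goes: bias is zero with no redos, with equal redos, with unblocked order and with even dropout. Bias needs both a trend and redo rates that differ by mealtime, and the documents report neither.

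A reader might go further and infer a trend from the protocol itself, because "Physical activity and sleep recommendations consistent with the American Academy of Pediatrics guidelines for adolescents will be encouraged" and staff make weekly calls that include CGM review. The documents do not support that. The same sentence adds that the advice is not formally prescribed, participants are told to keep their usual lifestyle, and the CGM is blinded. A uniform effect of advice would in any case be a period effect that random order balances. The expected retention of 75 to 80% does not establish imbalance either, since loss matters only if it is uneven.

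The reference to the literature under Statistical Consideration might imply a period term, and the word describing the mealtime comparison as univariate may mean one outcome at a time. Both readings are possible. Neither puts a period term on paper, and the Wilcoxon tests cannot carry one.

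Finally, the assumed trends are large for two weeks. Smaller trends shrink the precision loss with d² and the bias in proportion to d. What stands is that the analysis is under-specified and the redo rule has no counterpart in it.

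**Conclusion.** The omission is real: a three-period cross-over is analysed without a stated period or visit-order term, and redone visits have no defined place. The effect that follows from the omission alone, given a trend, is lost precision: an SE about 5 to 12% larger for trends of 0.3 to 0.5 within-person SD per visit, with conservative tests when order is balanced.

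It would be tempting to conclude that time trends do fall on the mealtime contrast. The documents do not show that. It is conditional on unequal redo rates: for a 20-point difference and these trends, the bias runs from 0.03 SD (shift 0.5, d = 0.3) to about 0.2 SD (shift 2, d = 0.5), and it grows in proportion to the difference. Trend, redo rates and timing of redos are all assumptions. The redo counts by mealtime, which the study team can tabulate, would show how far the second condition applies.

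**What to change.** - Fit actual visit order (period) as a fixed effect, with a participant random effect, in every mealtime model: profiles, log AUCs, insulinogenic index and hormones.
- Enter each redone visit at the position where it actually occurred, and say whether it replaces the first attempt.
- Report the number of redone visits by mealtime.
- Add a sensitivity analysis restricted to first-attempt visits. It should not become the main analysis: that would discard the results the redo option exists to recover, and AUC and the insulinogenic index need particular samples that an incomplete first attempt may lack.
- Label the Wilcoxon comparisons as unadjusted for visit order.

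The cost is two degrees of freedom for three positions, or three with a further class for later visits. In the simulation without a trend, the linear term moved the SE from 0.256 to 0.257 with equal 20% redo rates, from 0.257 to 0.263 at 10/10/30%, and from 0.257 to 0.287 in the most uneven case (0/0/50%). No new measurements are needed beyond the order of visits, which should be recoverable from the visit schedule. Because the Statistical analysis section is written in the past tense, the change may mean re-running the models as well as rewording the plan.

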Because of its simplicity, TRE may represent a more feasible approach for adolescents than other caloric restriction regimens. Our team recently conducted the first study examining the feasibility of TRE in adolescents with obesity. In this study, fifty adolescents were randomized to a self-selected 8-hour TRE compared to a prolonged eating window. TRE was found to be feasible, safe, and acceptable but there was no difference in glycemic profiles or weight loss between groups. These null findings may be due to the late eating window that was selected. To date, there have been no trial comparing early vs. late TRE on glycemic profiles in adolescents and it is unclear how meal-timing impacts glycemic profiles in youth. It remains unknown how the timing of meal consumption directly effects glycemic profiles and cardiometabolic endpoints in this age group. Thus, to address this question, in our proof-of-concept study, we aim to measure glycemic and metabolic responses to a test meal (controlled for macronutrient profile and caloric amount) at various meal-timings (early vs. afternoon vs. late) in thirty Latino adolescents (ages 13-19 years), with obesity, without diabetes. All participants will consume three standard test meals administered in random order at different times of day over a two-week period: (1) Early: test meal consumed at 8 AM; (2) Afternoon: 12 PM; (3) Late: 4 PM. Test meals will be consumed on different days at least three days apart after a minimum of a 16-hour fasting period. A continuous glucose monitor (CGM) will be placed on the participant for the duration of the 2-week period. The **primary endpoints** will be frequently sampled glucose, insulin, and c-peptide area under the curve (AUC) collected after consumption of a standard test meal, insulinogenic index (IGI: change in insulin/change in glucose over the first 30 min after the load), and glucose variability as captured by percent time in range on CGM. We **hypothesize** that adolescents with obesity will have reduced AUC and IGI following the later meals compared to the early meal. We will test these hypotheses with the following aims:

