Aim 1: Identify how timing of meal consumption after a prolonged 16-h fast affects glucose and insulin response in Latino adolescents with obesity. We will measure insulin secretion, clearance rates, and sensitivity assessed with a) 3-h frequent sampling of glucose, insulin, and c-peptide post meal, b) calculated insulinogenic index, and c) percent time in range measured by CGM. *We expect* that meal consumption at 12 and 4 PM will be associated with lower post prandial glucose excursions, decreased AUC and IGI, and increased percent time in range compared to that same meal consumed at 8 AM.

Aim 2: Examine the association between timing of meal consumption and incretin and pancreatic hormones in Latino adolescents with obesity. We will collect frequent sampling of glucagon, total GLP-1, GIP, and PP concentrations post-meal to explore how diurnal variation in these hormones impact insulin sensitivity. **We expect** that meal consumption at 12 and 4 PM will in greater change in incretin and pancreatic hormones concentrations compared to that same meals consumed at 8 AM.

Future Direction: The data collected during this pilot will inform the design of a randomized clinical trial to test the feasibility, safety, and efficacy of early vs. late TRE in adolescents with obesity to reduce glycemic and insulin response for the prevention of type 2 diabetes.

RESEARCH STRATEGY

i. Significance:

In the United States, 1 in 5 adolescents has obesity, and 30-50% of those go on to develop early onset type 2 diabetes. Increased pediatric obesity has been accompanied by a rising incidence of type 2 diabetes in adolescents, specifically among Latino youth. With increasing prevalence and increasing cost for care, obesity in adolescents is expected to result in extensive financial costs, and significant life limiting complications. In adolescents, conventional obesity treatment comprehensively addresses nutritional, physical activity, and behavioral topics with the goal of achieving clinically meaningful weight loss. Adherence to comprehensive lifestyle interventions is challenging for adolescents, in part because these approaches require frequent monitoring and engaging in multiple behavioral targets continuously. Therefore, there is a growing interest in simplifying intervention recommendations to decrease reliance on numeracy (Kilo calories and macronutrients), goal setting and complex skillsets. One simpler and promising approach is based on timing of eating.

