Aim 1: Identify how timing of meal consumption after a prolonged 16-h fast affects glucose and insulin response in Latino adolescents with obesity.

Quantifying glycemic profile after test meal from venous sample: Baseline and post-meal samples will be assayed for glucose, insulin, and c-peptide at times -10, , 10, , 30, , 60, 90, 120, and 180 minutes after the meal is consumed. The proposed protocol is modified to include multiple samples during the initial 30 minutes when glucose is rapidly increasing, allowing for modeling of glucose stimulated insulin secretion. Using this approach to model glucose kinetics without the need to administer insulin is a safe and cost-effective surrogate of β -cell function and can be more easily implemented in youth. Insulinogenic index (change in insulin/change in glucose over the first 30 min after the load) will be calculated. IGI has been widely used as an index of early phase insulin secretion in clinical studies. It is highly correlated with the acute insulin response on intravenous glucose tolerance test and is considered a reasonable surrogate.

Quantifying glycemic profile on CGM: Four parameters will be computed from CGM data for each test meal segment: Starting glucose: The glucose value at the start of the meal. Time to peak: The time difference between the start of the meal response and the meal response peak in minutes. Maximum glucose rise: The difference between the glucose levels at the start of the meal and post-meal peak in mg/dL. Glucose incremental area under curve: The positive

area under the post-meal glucose curve after subtracting the glucose value at the start. We will capture glucose readings every 5 minutes and obtain the weekly %TIR over the course of the study.

Aim 2: Examine the association between timing of meal consumption and incretin and pancreatic hormones in Latino adolescents with obesity to explore if the enhanced insulin secretion is secondary to corresponding variations in the release of incretin hormones.⁵¹

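### Does the log-scale analysis of the insulinogenic index need a written rule for ratios that are zero, negative, undefined or formed by two falls?

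*Combined protocol and SAP*

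**What the plan says.** Specific Aims and the study design overview list IGI among the primary endpoints. The Aim 1 measurement text defines it: "Insulinogenic index (change in insulin/change in glucose over the first 30 min after the load) will be calculated". Neither place requires the two changes to be positive or sets a smallest usable glucose change. Aim 1 expects the later meals to show "lower post prandial glucose excursions, decreased AUC and IGI".

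The Statistical analysis section at the end of the document, written in the past tense, gives skewness as the reason for the log: "differences in glucose, insulin, and c-peptide AUCs over 180 minutes and the insulinogenic index by mealtime were assessed on a logarithmic scale". It names the glucose, insulin and c-peptide profiles as the primary outcome variables and does not list IGI there.

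The protocol's Statistical Consideration paragraph is broader. It plans graphical checks, outlier identification and a ladder-of-powers search for a transformation, and it adds: "The statistical approach will be implemented with and without transformations when appropriate". It also says: "Wilcoxon matched paired test will be used for tests of significance between variables obtained during morning, afternoon, and evening meal ingestion". These provisions cover outcomes in general and do not mention IGI. The option to repeat a visit applies to missing laboratory results, not to an unusable ratio from complete results.

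**The concern.** A ratio of two signed changes does not suit a logarithm in every case, and two separate things can go wrong.

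- **Selection by outcome.** A visit where insulin or glucose fails to rise has no log-IGI and drops out because of its own result. If the early glucose rise differs by mealtime, the losses differ too, and the mealtime contrast rests on a selected set of visits.
- **False positives in the ratio.** If insulin and glucose both fall, the ratio is positive and enters the model as an ordinary response. This happens on any scale, so an untransformed or rank analysis does not cure it.

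IGI carries a directional hypothesis. A shift that differed by mealtime could shrink or imitate the expected fall, and a reader given only a percent change would not know which visits it rested on.

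**Working it through.** **1. Sign cases (arithmetic only; illustrative insulin and glucose changes).**

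| Insulin change | Glucose change | IGI | log IGI |
|---|---|---|---|
| 40 | 20 | 2.0 | 0.693 |
| 40 | -2 | -20 | none |
| -5 | 10 | -0.5 | none |
| 0 | 10 | 0 | none |
| 40 | 0 | undefined | none |
| -5 | -2 | +2.5 | 0.916 |
| 40 | 1 | 40 | 3.689 |

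The algebra of the concern is correct. The last row also shows why a log is a reasonable choice: a small denominator inflates the raw ratio 20-fold (40/2), and the log pulls it in.

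**2. How often? The documents give no count, mean or SD.** What they do give points to few such visits: the meal lists 84 + 17 + 16 = 117 g of carbohydrate, and the Aim 1 text describes the first 30 minutes as a time of rapidly increasing glucose.

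**3. Possible size, all inputs assumed.** Model: insulin change = 2 × glucose change + normal error, so true IGI is 2 at both mealtimes. Central setting: mean glucose rise 30 mg/dL at 8 AM and 20 at 4 PM, SD 15, insulin error SD 25, 30 participants, paired comparison of log-IGI.

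- No glucose rise: Φ(-30/15) = 2.3% at 8 AM and Φ(-20/15) = 9.1% at 4 PM.
- No insulin rise: the SD is √(4×15² + 25²) = √1525 = 39.1, giving Φ(-60/39.1) = 6.2% and Φ(-40/39.1) = 15.3%.
- Result: 1.7 against 3.5 of 30 visits have no log, and 0.5 against 1.9 are two-fall. The 4 PM/8 AM ratio is 1.06 to 1.07 over repeated runs. Bias/SE is 0.067/0.18 = 0.37, and null rejection is 5.7% against a nominal 5%.

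Other settings (8 AM rise, 4 PM rise, glucose SD, insulin error SD):

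| Setting | Ratio |
|---|---|
| 30, 20, 15, 40 | 1.14 |
| 25, 15, 15, 25 | 1.10 |
| 40, 30, 20, 25 | 1.02 to 1.03 |
| 30, 30, 15, 25 (equal rises) | 1.00 |
| 30, 20, 3, 5 (nothing lost) | 0.995 |
| 50, 40, 15, 25 | 0.98 |
| 40, 30, 12, 15 | 0.99 |
| 30, 20, 8, 10 | 0.98 |

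An upward shift needs settings where roughly 10-22% of 4 PM visits show no insulin rise after this meal. With few losses the shift is slightly downward even though the rises differ. Excluding two-fall ratios cuts the central shift to about 4%, but moves the three low-loss settings at the foot of the table slightly further from 1. No single sign or size can be claimed.

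**4. Would a replacement analysis do better?** One candidate is log(insulin AUC 0-30 / glucose AUC 0-30), which can always be computed and uses the early AUCs of the Statistical Consideration paragraph. With a linear rise of mean m, fasting glucose 90 and fasting insulin F (both assumed), the ratio is (30F + 15×2m)/(30×90 + 15m).

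- F = 10: 4 PM (300 + 600)/(2700 + 300) = 0.300; 8 AM (300 + 900)/(2700 + 450) = 0.381; quotient 0.79.
- F = 40: 1800/3000 = 0.600; 2100/3150 = 0.667; quotient 0.90.

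So with equal IGI it is 10-21% lower at 4 PM, in the hypothesised direction, which is more than the 6-7% it was meant to guard against. A model of insulin change adjusted for glucose change fares no better as a substitute. A glucose error SD of 5 mg/dL gives a spurious 4 PM effect of about -3.6 to -4.0 insulin units, against an expected change of 2×20 = 40.

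**The case for a change.** The strongest case for a change is that the defect is algebraic and needs no simulation. Specific Aims calls IGI primary, the closing section names one analysis for it, and that analysis cannot be computed for some possible values and accepts others that are meaningless. The protocol's untransformed and Wilcoxon analyses are generic. They cannot use an undefined ratio, they do not correct a two-fall ratio, and they would rank a negative ratio caused by a glucose fall lowest even when insulin rose. In the central setting a true 20% fall would be estimated as about 13% (ratio 0.873). Stating a rule and a count would cost almost nothing.

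Most of this is right. The documents contain no rule, and the general provisions only partly fill the gap. What does not stand is the step from a missing detail to a bias. Nothing in the documents shows that a single affected visit exists, and the 13% figure comes from a high-loss setting. The simulation is also a two-mealtime paired test, whereas the plan uses a mixed-effects model over three mealtimes. That model keeps a participant's other usable visits, so the simulated loss of pairs does not describe the plan. What remains is a request to state a rule and report counts, which is ordinary reporting.

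**Conclusion.** No change to the plan follows. The gap is genuine, but it is one that analysts fill sensibly. The closing section says the outcome distributions were examined descriptively and graphically, and a visit with no log-IGI shows up as a shortfall in the number analysed. A two-fall ratio does not announce itself in that way, but it is found by looking at the two changes that form the ratio, which the analyst must compute anyway. The log scale is a fair choice for a skewed ratio, and neither alternative examined is a better method.

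On assumed inputs the effect on a mealtime contrast lies between about -2% and +14%, at most 0.56 of a standard error with 30 participants. It is zero when the early glucose rises are equal. These figures rest on a zero-intercept linear model with normal errors and on means and SDs that the documents do not give, so they bound plausibility and do not estimate a bias. The conclusion would be different if the data showed many visits with no early rise, unevenly spread over mealtimes; nothing in the documents suggests that.
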